10.2.5 SAEs (Including Deaths) and Adverse Events Leading to Study Drug Discontinuation

SAEs (including deaths) and AEs leading to study drug discontinuation will be summarized by SOC and PT and in listing format for SAS-CREON-ABT and SAS-CREON-SPL.

10.2.6 Adverse Events of Special Interest

Adverse events of special interest will be summarized by SOC and PT. The following TEAEs compatible with clinical symptoms of EPI will be considered as Adverse Events of Special Interest (AESI) for this study:

- Diarrhea
- Abdominal pain
- Abdominal bloating
- Flatulence
- Steatorrhea

Detailed information about the search criteria is in Appendix B.

Tabular listings of adverse events of special interest will be provided.

10.3 Analysis of Laboratory Data

Laboratory data are not collected prospectively during the treatment period. No laboratory analysis is planned.

10.4 Analysis of Vital Signs

Vital sign data are not collected prospectively during the treatment period. No vital sign analysis is planned.

11.0 Interim Analysis

No formal interim analysis is planned.

11.1 Data Monitoring Committee

An external data monitoring committee (DMC) composed of persons independent of AbbVie and with relevant expertise in their field will review safety data from the ongoing study. The primary responsibility of the DMC will be to protect the safety of the subjects participating in this study.

A separate DMC charter describes the roles and responsibilities of the DMC members, frequency of data reviews, relevant data to be assessed, and general operations.

12.0 Overall Type-I Error Control

Since there are no efficacy analyses for early stopping planned for the DMC review, or formal statistical hypothesis testing, alpha spending is not applicable.

There are pharmacodynamic endpoints analyzed descriptively. Multiplicity adjustment is not planned for analyses.

13.0 Version History

Table 2. SAP Version History Summary

Version	Date	Summary		
1.0	07 Dec 2021	Original version		
2.0	20 Jul 2023	 Major updates: Section 9.4.2 - Sensitivity analysis for events of accidentally breaking blindness. Section 10.2.1 - In the cases that an AE happens in a day that a subject takes both CREON-ABT and CREON-SPL, such AE will be counted under CREON-SPL. 		

[figure not shown]

Appendix A. Protocol Deviations

[figure not shown]
The number and percentage of subjects for each category in the collected data for protocol deviation will be summarized.

Appendix B. Definition of Adverse Events of Special Interest

Adverse Events of Special Interest (AESI) will be identified using the following search criteria:

[figure not shown]
Adverse Event of Special Interest	Preferred Terms
Diarrhea	Diarrhoea
	Diarrhoea haemorrhagic
	 Diarrhoea infectious
	Defaecation urgency
	 Frequent bowel movements
	 Gastrointestinal hypermotility
	 Faecal volume increased
	 Overflow diarrhoea
Abdominal pain	Abdominal discomfort
	Abdominal Pain
	 Abdominal pain lower
	 Abdominal pain upper
	Gastrointestinal pain
Abdominal bloating	Abdominal distension
	 Gastrointestinal sounds abnormal
Flatulence	Flatulence
Steatorrhea	Faeces pale
	Faecal fat increased
	Faeces discoloured

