5 STUDY ACTIVITIES

5.1 Eligibility Criteria

Subjects must meet all of the following criteria in order to be enrolled in the study. Anything other than a positive response to the questions below will result in exclusion from study participation.

Consent

1. Subjects must voluntarily sign and date an informed consent form (ICF), approved by an independent ethics committee (IEC)/institutional review board (IRB), prior to the initiation of any screening or study-specific procedures. The use of Legally Authorized Representatives (LARs) is prohibited for this protocol.

Demographic

- 2. Adult male or female, at least 18 years old at the time of ICF signature.
- 3. Are willing and able to comply with all procedures required in this protocol.
- 4. Subject must be able to read, and must be willing and capable to use the electronic patient reported outcome (ePRO) device and the platform needed for remote assessment and telemedicine visits.

Disease/Condition Activity

- 5. Subject has a previous diagnosis of Cystic Fibrosis (CF) or Chronic Pancreatitis (CP).
 - A diagnosis of CF is defined by:
 - sweat chloride test result ≥ 60 mmol/L, and/or
 - documented CF-causing CFTR mutations and clinical features of CF.^{8,9}
 - A diagnosis of CP is defined by presence of definite or probable evidence of CP in a patient with history and physical examination suspicious for CP, as described in the 2014 APA Practice Guidelines in CP.¹⁰
- 6. Subject has a previous diagnosis of EPI that is currently clinically controlled (no clinically overt steatorrhea or diarrhea) with a Creon dosing regimen for more than 3 months prior to Screening.
- 7. Subject has a Total Symptom Score (TSS) < 1.8 on PEI-Q at Screening.

Subject History

- 8. Subject is on an individualized, stable (no change in the prescribed total daily dose in LU for at least 3 months before Screening) dose regimen of commercially available Creon that includes the use of the 24,000 LU capsule strength (up to a maximum of sixteen 24,000 LU capsules per day). The subject's total daily dose should not exceed 4,000 LU/g fat/day or 10,000 LU/kg/day.
- 9. Subject does not have any medical history of any type of malignancy involving the digestive tract in the last 5 years, nor any of the following medical conditions:

At any time prior to Screening:

- fibrosing colonopathy
- celiac disease
- bariatric surgery or partial/total gastrectomy
- inflammatory bowel disease
- irritable bowel syndrome

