Important Medical Event Requiring Medical or Surgical Intervention to Prevent Serious Outcome	An important medical event that may not be immediately life-threatening or result in death or hospitalization, but based on medical judgment may jeopardize the subject and may require medical or surgical intervention to prevent any of the outcomes listed above (i.e., death of subject, life threatening, hospitalization, prolongation of hospitalization, congenital anomaly, or persistent or significant disability/incapacity). Additionally, any elective or spontaneous abortion or stillbirth is considered an important medical event.

All AEs reported from the time of first study drug administration until 30 days after discontinuation of study drug administration will be collected, whether solicited or spontaneously reported by the subject. In addition, study procedure-related serious and nonserious AEs will be collected from the time the subject signs the study-specific informed consent.

Adverse events will be monitored throughout the study to identify any of special interest for this study.

Adverse Events of Special Interest

The following TEAEs compatible with clinical symptoms of EPI will be considered AESI for this study:

- Diarrhea
- Abdominal pain
- Abdominal bloating
- Flatulence
- Steatorrhea

Patients with signs and symptoms suggestive of worsening EPI should be evaluated and treated as clinically indicated by the investigator.

Adverse Event Severity and Relationship to Study Drug

The investigators will rate the severity of each AE as mild, moderate, or severe.

The investigator will use the following definitions to rate the severity of each AE:

Mild The adverse event is transient and easily tolerated by the subject.

Moderate The adverse event causes the subject discomfort and interrupts the subject's

usual activities.

Severe The adverse event causes considerable interference with the subject's usual

activities and may be incapacitating or life threatening.

The investigator will use the following definitions to assess the relationship of the AE to the use of study drug:

ReasonablePossibility
After consideration of factors including timing of the event, biologic plausibility, clinical judgment, and potential alternative causes, there is sufficient evidence (information) to suggest a causal relationship to Creon

24,000 LU dispensed as CREON-ABT or CREON-SPL.

No Reasonable Possibility

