3.2 Safety Endpoint(s)

Safety evaluations include monitoring of treatment-emergent adverse events (TEAEs).

A TEAE compatible with the clinical symptoms of EPI will be considered an adverse event of special interest (AESI) for this study and will be summarized separately.

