10.2 Adverse Events

Per the study protocol, all AEs (non-serious and serious) reported from the time of study drug administration until 30 days post discontinuation of study drug administration will be

collected. In addition, AEs related to study procedures (non-serious and serious) will be collected from the time the subject signed the study-specific informed consent.

All Adverse events (AEs) and Serious Adverse events (SAEs) will be summarized and presented using primary MedDRA System Organ Classes (SOCs) and preferred terms (PTs) coded according to the version of the MedDRA coding dictionary used for the study at the time of database lock. The actual version of the MedDRA coding dictionary used will be noted in the AE tables and in the clinical study report. Specific adverse events will be counted once for each subject for calculating percentages, unless stated otherwise. In addition, if the same adverse event occurs multiple times within a subject, the highest severity and level of relationship to investigational product will be reported.

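### The AESIs are named by symptom but selected only by a closed preferred-term list, which has no own-name term for steatorrhea or abdominal bloating and no rule for reports that code elsewhere (minor)

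*SAP*

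**What the plan says.** Protocol 6.1 introduces five symptoms with the words "The following TEAEs compatible with clinical symptoms of EPI will be considered AESI for this study". SAP 10.2.6 repeats the same five: "The following TEAEs compatible with clinical symptoms of EPI will be considered as Adverse Events of Special Interest (AESI) for this study". SAP 3.2 makes them part of the safety endpoint: "A TEAE compatible with the clinical symptoms of EPI will be considered an adverse event of special interest (AESI) for this study", to be summarized separately.

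For the operational rule, SAP 10.2.6 says: "Detailed information about the search criteria is in Appendix B". Appendix B opens with "Adverse Events of Special Interest (AESI) will be identified using the following search criteria" and sets preferred terms against each of the five symptoms. The steatorrhea row holds *Faeces pale*, "Faecal fat increased" and *Faeces discoloured*. The abdominal bloating row holds *Abdominal distension* and *Gastrointestinal sounds abnormal*.

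On coding, SAP 10.2 says that events are "coded according to the version of the MedDRA coding dictionary used for the study at the time of database lock". Neither document names the version or reproduces dictionary content.

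**The concern.** The definition and the selection rule work on different things. SAP 10.2.6 and Protocol 6.1 say which events are of special interest by naming symptoms. Appendix B picks them out by coded term alone. The two agree only if every report of a named symptom codes to a listed term, and nothing in the SAP says what happens if one does not.

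Steatorrhea is the row most worth checking. Investigators are given the word itself: entry criterion 6 in Protocol 5.1 requires EPI to be controlled, with "no clinically overt steatorrhea or diarrhea". A new report after the switch to CREON-SPL is therefore one of the changes that the AESI summary is there to show. Protocol 4.2 says the design avoids stool collection, and SAP 10.3 says no laboratory data are collected prospectively during treatment. Such events are thus likely to arrive as reported symptoms and not as measured faecal fat.

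At stake is whether the AESI outputs contain every event that the SAP says they contain. The PEI-Q analyses do not depend on it, and no hypothesis is tested.

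**Working it through.** The plan gives no figure to reproduce here. The check is a comparison of text with a few counts.

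**1. Terms in Appendix B, by row**

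| Named symptom | Preferred terms | Own-name term listed? |
|---|---|---|
| Diarrhea | 8 | Yes |
| Abdominal pain | 5 | Yes |
| Abdominal bloating | 2 | No |
| Flatulence | 1 | Yes |
| Steatorrhea | 3 | No |

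The total is 8 + 5 + 2 + 1 + 3 = 19. British and American spellings were treated as the same. No term in any row contains the stem *steat*.

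**2. Other routes into the AESI outputs.** There are none. Protocol 6.1 requires an EPI Symptom CRF for treatment-emergent events compatible with EPI symptoms, but no analysis section of either document uses that form to select AESIs. Neither document has a rule based on the reported term.

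**3. What follows under each coding outcome**
- If reports of steatorrhea and bloating code to listed terms, definition and search agree and no event is missed.
- If a report of either codes outside the list, SAP 10.2.6 calls it an AESI and Appendix B does not find it.

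The documents do not show which outcome applies.

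**4. Where an unmatched event would be absent.** SAP 10.2.2 has 10 overview lines, of which 2 concern AESIs (all, and those with a reasonable possibility of relationship). The overview is produced in 3 versions: main, first 28 days, and per 100 patient-years. SAP 10.2.6 adds one table by SOC and PT, and the listing.
- Onset within 28 days, reasonable possibility: 2 × 3 + 2 = 8 places
- Onset within 28 days, no reasonable possibility: 1 × 3 + 2 = 5
- Onset later, reasonable possibility: 2 × 2 + 2 = 6
- Onset later, no reasonable possibility: 1 × 2 + 2 = 4

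This shows how far one event would reach through repeated displays. It is not a size of error.

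**5. Scale of one subject.** The CREON-SPL safety set (SAS-CREON-SPL) requires at least one dose of CREON-SPL, so it cannot exceed the approximately 30 subjects enrolled at the Run-in Visit. One subject is therefore at least 1/30 = 3.3 percentage points. If the set were as small as 24 (an assumption: the whole 20% dropout occurs before CREON-SPL starts), it would be 1/24 = 4.2 percentage points. Either figure applies only if that subject has no other listed AESI.

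**The case against.** The strongest reply is that Appendix B is itself the definition. Its title says so, and SAP 10.2.6 refers to it for detail, so the five names are category labels and the term list gives them content. A search by preferred term also suits outputs tabulated by SOC and PT. On this reading the steatorrhea row is a deliberate mapping to descriptions of the sign, just as bloating is mapped to distension. That reading is reasonable, and it means that a missing name is not in itself an error. It does not remove the gap: SAP 10.2.6 still says that the named events count, and the mapping is complete only if the dictionary sends every such report to a listed term.

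A reader might infer more: that a steatorrhea preferred term exists and was overlooked, so that events will be lost. The documents do not support this. They contain no dictionary content, bloating lacks an own-name term as well, and a term may have dropped out of the table when the SAP was converted to text. The row shows no visible gap, but the neighbouring PEI-Q appendix did lose content.

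It would also be too strong to say that safety information would disappear. An unmatched event would remain in the treatment-emergent tables by SOC and PT (SAP 10.2.1 and 10.2.3), and it should trigger an EPI Symptom CRF. Stool symptoms also feed the PEI-Q bowel movement score. These points stand, and they limit the consequence to misclassification within the adverse event reporting.

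**Conclusion.** The mismatch is real and minor. The AESIs are defined by five symptoms and found only through 19 preferred terms. Two of the symptoms have no own-name term, and no rule covers a report that codes elsewhere. That an event would be missed is an assumption, not a finding: it requires a report of steatorrhea or bloating to code outside the list in the MedDRA version at database lock.

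No net error can be stated, because the documents give neither an expected number of such events nor their coding. If the check shows that both symptoms code to listed terms, or that the original table holds a term missing from the text copy, no event is missed and only a clarification remains.

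**What to change.** Before the AESI outputs are run:

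1. Check each Appendix B row against the MedDRA version used at database lock, and add any same-named preferred term that is missing, in particular for steatorrhea.
2. Add one sentence to Appendix B: a treatment-emergent event reported as any of the five named symptoms counts as an AESI whatever its coded term. The sentence should cover all five. A rule for steatorrhea alone would select one AESI by reported term and the other four by code.

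A comparison with the completed EPI Symptom CRFs would be a useful extra check but is optional.

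The cost is one dictionary check, one sentence in the SAP and a short review of reported terms. No new data are needed, and the PEI-Q analyses and general adverse event tables do not change.

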Appendix C. Pancreatic Exocrine Insufficiency Questionnaire (PEI-Q)

This questionnaire asks about problems you may experience if you do not produce enough enzymes to digest your food.

AB	DOMINAL SYMPTOMS	NO NOT AT ALL	YES, A LITTLE BIT	YES, SOME	YES, QUITE A BIT	YES, A LOT	SCORE	
1.	In the past 7 days, did you have stomach pain?	0	1	2	3	4		
2.	In the past 7 days, did you feel bloated (your stomach feeling tight and full)?	0	1	2	3	4		
3.	In the past 7 days, did your stomach make noises?	0	1	2	3	4		
4.	In the past 7 days, did you pass gas?	0	1	2	3	4		
5.	In the past 7 days, when you passed gas did it smell bad?	0	1	2	3	4		
6.	In the past 7 days, did you feel sick (but didn't actually vomit/throw up)?	0	1	2	3	4		
7.	In the past 7 days, did you have a lack of appetite?	0	1	2	3	4		
		Sum of abdominal symptom scores:						
	Mean abdominal symptom domain score (A):							
во	WEL MOVEMENT SYMPTOMS	NO NOT AT ALL	YES, A LITTLE BIT	YES, SOME	YES, QUITE A BIT	YES, A LOT	SCORE	
BC 8.	WEL MOVEMENT SYMPTOMS In the past 7 days, did you have diarrhea (watery poo)?						SCORE	
	In the past 7 days, did you have diarrhea	AT ALL	LITTLE BIT	SOME	A BIT	A LOT	SCORE	
8. 9.	In the past 7 days, did you have diarrhea (watery poo)? In the past 7 days, did you feel the need to rush to the toilet to have a bowel	AT ALL 0	LITTLÉ BIT	SOME 2	A BIT	A LOT	SCORE	
8.9.10.	In the past 7 days, did you have diarrhea (watery poo)? In the past 7 days, did you feel the need to rush to the toilet to have a bowel movement (have a poo)? In the past 7 days, did your poo look	0 0 0	1 1	SOME 2	3 3	4 4	SCORE	
8.9.10.11.	In the past 7 days, did you have diarrhea (watery poo)? In the past 7 days, did you feel the need to rush to the toilet to have a bowel movement (have a poo)? In the past 7 days, did your poo look lighter or orange in color? In the past 7 days, when you had a poo	0 0 0 0 0 0 0 0 0 0 0 0 0 0 0 0 0 0 0		2 2 2	3 3 3 3	4 4 4	SCORE	
8.9.10.11.	In the past 7 days, did you have diarrhea (watery poo)? In the past 7 days, did you feel the need to rush to the toilet to have a bowel movement (have a poo)? In the past 7 days, did your poo look lighter or orange in color? In the past 7 days, when you had a poo did it smell bad? In the past 7 days, did you see or have fat	0 0 0 0 0 0 0 0 0 0 0 0 0 0 0 0 0 0 0		2 2 2 2 2	3 3 3 3 3 3 3 3 3 3 3 3 3 3 3 3 3 3 3	4 4 4 4	SCORE	

18. In the past 7 days, did your **enzyme problems** affect your **social activities**?

	Version 2.0 – 20 July 2023						_
	Sum of bowel movement symptom scores:						
	Mean bowel movement symptom score (B):						
	MEAN TOTAL SYMPTOM SCORE ([A+B]/2):						
Only complete if you have been diagnosed with Pancreatic Exocrine Insufficiency (PEI)							
IM	PACTS	NO NOT AT ALL	YES, A LITTLE OF THE TIME	YES, SOMETIMES	YES, MOST OF THE TIME	YES, ALL OF THE TIME	SCORE
14.	In the past 7 days, did you avoid fatty food ?	0	1	2	3	4	
15.	In the past 7 days, did your enzyme problems affect your ability to concentrate?	o	1	2	3	4	
		NO NOT AT ALL	YES, A LITTLE BIT	YES, MODERATELY	YES, QUITE A BIT	YES, EXTREMELY	SCORE
16.	In the past 7 days, did you feel embarrassed going to the toilet because of your enzyme problems?	0	1	2	3	4	
17.	In the past 7 days, did you feel worried, anxious or stressed because of your enzyme problems?	0	1	2	3	4	

YES, A

LITTLE OF

THE TIME

NO NOT

AT ALL

YES,

SOMETIMES

YES,

MOST OF

THE TIME

YES,

ALL OF

THE TIME

Sum of impact scores:

Mean impact domain score (C):

SCORE
